#### 8.2.7.2. Treatment of Hyperglycemia and Hypoglycemia during In-house Periods

Hypoglycemia during MMTT:

Participants will be without food intake from the start of the MMTT to completion of blood collection (approximately 240 minutes) unless required to treat Level 1 hypoglycemia with symptoms or Level 2 hypoglycemia. If it occurs, treatment is to be done with either rapidly absorbable oral carbohydrates or intravenous glucose.

Hypoglycemia during Exercise:

If hypoglycemia ensues **CC** will be treated initially with ~**CC** of oral carbohydrates. If the glucose level after approximately **CC** minutes, up to an additional **CC** of oral carbohydrates can be provided. Repeat as necessary if glucose value remains below **CC** mg/dL. The same approach should be used if hypoglycemia ensues after completion of the exercise prior to the MMTT. The administration of the MMTT could be given minutes earlier to prevent hypoglycemia at the discretion of the investigator.

If carbohydrates are administered and consumed during the in-house periods, it must be captured in the eCRF.

If a patient is experiencing hyperglycemia (glucose level **CC** for more than hour, insulin glulisine will be administered intravenously.

In cases where treatment of either hypo- or hyperglycemia require intervention, samples for glucose will be taken and PK samples will be collected as planned.

## 8.2.8. Rating of Perceived Exertion

The RPE scale will be used during each of the exercise periods as outlined in the SoA (Section 1.3). The **CCI** is a well-validated tool **CCI** to assess perceived physical effort during exercise; it is presented as a scale **CCI** anchored by verbal descriptors. This scale describes different efforts: is no exertion at all and it the maximal exertion or hardest possible effort. Participants will be asked to point to a number that best describes their feelings of the exercise at that moment.

# 8.3. Adverse Events, Serious Adverse Events, and Product Complaints

The definitions of the following events can be found in Appendix 3 (Section 10.3):

- AEs
- SAEs, and
- product complaints

These events will be reported by the participant (or, when appropriate, by a caregiver, surrogate, or the participant's legally authorized representative).

The investigator and any qualified designees are responsible for detecting, documenting, and recording events that meet these definitions and remain responsible for following up events that are serious, considered related to the study intervention or study procedures, or that caused the participant to discontinue the study (see Section 7).

Care will be taken not to introduce bias while detecting events. Open-ended and nonleading verbal questioning of the participant is the preferred method to inquire about event occurrences.

After the initial report, the investigator is required to proactively follow up each participant at subsequent visits/contacts. All SAEs will be followed up until resolution, stabilization, the event is otherwise explained, or the participant is lost to follow-up (as defined in Section 7.3). For product complaints, the investigator is responsible for ensuring that follow-up includes any supplemental investigations as indicated to elucidate the nature and/or causality. Further information on follow-up procedures is provided in Appendix 3 (Section 10.3).

Investigators are responsible for monitoring the safety of participants who have entered this study and for alerting Lilly or its designee to any event that seems unusual, even if this event may be considered an unanticipated benefit to the participant.

The investigator is responsible for the appropriate medical care of participants during the study.

## 8.3.1. Timing and Mechanism for Collecting Events

This table describes the timing, deadlines, and mechanism for collecting events.

Event	Collection Start	Collection Stop	Timing for Reporting to Sponsor or Designee	Mechanism for Reporting	Back-up Method of Reporting
Adverse Event					
AE	Signing of the ICF	The follow- up visit	As soon as possible upon site awareness	AE CRF	N/A
Serious Adverse	Event				
SAE and SAE updates – prior to start of study intervention and deemed reasonably possibly related with study procedures	Signing of the ICF	Start of intervention	Within 24 hours of awareness	SAE paper form	SAE paper form
SAE and SAE updates – after start of study intervention	Start of intervention	participation in study has ended	Within 24 hours of awareness	SAE paper form	SAE paper form
SAE* – after participant's study participation has ended and the investigator becomes aware	After participant's study participation has ended	N/A	Promptly	SAE paper form	N/A
Pregnancy					
Pregnancy in female participants and female partners of male participants	After the start of study intervention	10 hours after the last dose	Within 24 hours of learning of the pregnancy (see Section 8.3.2)	Pregnancy paper form	Pregnancy paper form

Event	Collection Start	Collection Stop	Timing for Reporting to Sponsor or Designee	Mechanism for Reporting	Back-up Method of Reporting
Product Complai	ints		-	_	
PC associated with an SAE or might have led to an SAE	Start of study intervention	End-of-study intervention	Within 24 hours of awareness	Product Complaint form	N/A
PC not associated with an SAE	Start of study intervention	End- of-study intervention	Within 1 business day of awareness	Product Complaint form	N/A
Updated PC information			As soon as possible upon site awareness	Originally completed Product Complaint form with all changes signed and dated by the investigator	N/A
PC (if investigator becomes aware)	Participation in study has ended	N/A	Promptly	Product Complaint form	

Abbreviations: AE = adverse event; CRF = case report form; ICF = informed consent form; N/A = not applicable; PC = product complaint; SAE = serious adverse event.

\* SAEs should not be reported unless the investigator deems them to be possibly related to study treatment or study participation.

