#### **Data Monitoring Committee: No**

# 1.2. Schema

# **1.3.** Schedule of Activities (SoA)

# **1.3.1.** Overall Schedule

Procedure	Sc	creening Period	Study Period		Follow- up/ED	Comments	
Visit Number	1	Optional visits	2	3, 4,	5, 6	7	
	Screening	Basal rate optimization	Assessment	In-h	ouse		
Timing	Within Sel days prior to Visit 3	First evaluation - Within days of screening visit Second evaluation - Within days of screening visit	days prior to Visit 3	days		after Visit 6	
Day		CC					
In-house stay				X	X		
Admission to CRU				Х			
Discharge from CRU					Х		At the discretion of investigator
Outpatient	Х	Х	Х			X	
Informed consent	Х						
Inclusion and exclusion criteria	Х			Xa			
Fasting	Х				Х		
Demographic data	Х						
Smoking and alcohol consumption habits	Х						
Medical history	Х						
Weight, height, BMI	X			X b		Xb	
Physical examination	X			Х		X	
Vital signs	X			Х		X	
12-lead ECG	X						Single

Procedure	Sci	reening Period	Study Period		Follow- up/ED	Comments	
Visit Number	1	Optional visits	2	3, 4, 5, 6		7	
	Screening	Basal rate optimization	Assessment	In-ho	ouse		
Timing	Within days prior to Visit 3	First evaluation - Within days of screening visit Second evaluation - Within days of screening visit	days prior to Visit 3	days		after Visit 6	
Day		CCI					
In-house stay				X	X		
Clinical Laboratory Tests	Х						See Section 10.2
HbA1c	Х						
Fasting C-peptide	Х						
Pregnancy test (females only)	Х			Х		Х	Serum test at screening; urine pregnancy test prior to study treatment and at follow-up; See Section 10.4.2
Urine drug screen and ethanol testing	Х		Х	Х			Ethanol breath test on Day -1 and assessment day.
Perform pump basal rate assessment, review and titration if needed	X	X°					Collect and review the ambulatory glucose profile, pump settings, etc. Once established, these rates should be maintained for all study periods
Dispense study diaries and complete training	Х						

Procedure	Sci	reening Period	Study Period		Follow-	Comments	
Visit Number	1 Screening	Optional visits Basal rate optimization	2 Assessment	3, 4, In-h(	5, 6	7	
Timing	Within days prior to Visit 3	First evaluation - Within days of screening visit Second evaluation - Within days of screening visit	days prior to Visit 3	a da	iys	after Visit 6	
Day							
In-house stay				X	X		
Collect, review, and discuss entries in study diaries		Х	Х	Х		Х	

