### 4.1.5. Follow-Up Visit

Participants will be required to visit CRU 3 to 7 days after Visit 6 and will undergo assessments as mentioned in Section 1.3.1. The diary will be reviewed and checked for hypoglycemic events and AEs.

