## 8.3.2. Pregnancy

#### **Collection of pregnancy information**

Female participants who become pregnant

- The investigator will collect pregnancy information on any female participant who becomes pregnant while participating in this study. The initial information will be recorded on the appropriate form and submitted to the sponsor within 24 hours of learning of a participant's pregnancy.
- The participant will be followed up to determine the outcome of the pregnancy. The investigator will collect follow-up information on the participant and the neonate, and the information will be forwarded to the sponsor. Generally, followup will not be required for longer than 6 to 8 weeks beyond the estimated delivery date. Any termination of pregnancy will be reported, regardless of gestational age, fetal status (presence or absence of anomalies) or indication for the procedure.

- While pregnancy itself is not considered to be an AE or SAE, any pregnancy complication or elective termination of a pregnancy for medical reasons will be reported as an AE or SAE.
- Any poststudy pregnancy-related SAE considered reasonably related to the study intervention by the investigator will be reported to the sponsor as described in Section 8.3.1. While the investigator is not obligated to actively seek this information in former study participants, he or she may learn of an SAE through spontaneous reporting.
- Any female participant who becomes pregnant while participating in the study will discontinue study intervention. If the participant is discontinued from the study, follow the standard discontinuation process and continue directly to the follow-up phase. The follow-up on the pregnancy outcome should continue independent of intervention or study discontinuation.

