# WOCBPs who are NOT completely abstinent as their preferred and usual lifestyle, or in a same-sex relationship, as part of their preferred and usual lifestyle

Торіс	Explanation	
Pregnancy testing	Negative serum result at screening followed by a negative urine result prior to study treatment and at follow-up.	
	Note: subsequent pregnancy testing is compound specific	
Contraception	Agree to use 2 forms of effective contraception, where at least 1 form must be highly effective (less than 1% failure rate)	

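### The pregnancy collection stop in Protocol 8.3.1 conflicts with the follow-up pregnancy test and with Section 8.3.2

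*Protocol*

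**What the plan says.** Four places in the current protocol bear on when pregnancy collection ends.

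- **Section 8.3.1, event table.** The pregnancy row covers female participants and female partners of male participants. Collection starts "After the start of study intervention" and stops "10 hours after the last dose". The reporting deadline is 24 hours from learning of the pregnancy, and the row refers the reader to Section 8.3.2.
- **Section 8.3.2.** The investigator collects information on "any female participant who becomes pregnant while participating in this study", reports it within 24 hours of learning of it, and follows the pregnancy to outcome whether or not the participant has left the intervention or the study. The text addresses female participants only.
- **Section 1.3.1, comment on the pregnancy test row, and Section 10.4.2.** The schedule asks for a "urine pregnancy test prior to study treatment and at follow-up". The contraception guidance requires a negative serum result at screening, "followed by a negative urine result prior to study treatment and at follow-up".
- **Section 4.1.5.** "Participants will be required to visit CRU 3 to 7 days after Visit 6".

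On product complaints, both ordinary rows of the 8.3.1 table stop at the end of study intervention. A later row, for complaints the investigator happens to learn of, starts only when participation has ended. The schedule in 1.3.1 nevertheless marks product complaints for collection at Visit 7.

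**The concern.** A collection window should contain the assessments scheduled to find the event. Here the table closes the pregnancy window within hours of the last study insulin, while the protocol plans a test days later. The section that the row cites sets a different and wider scope. A site following the table and a site following 8.3.2 could handle a positive follow-up test differently, and nothing says which text prevails. At stake are consistent and timely reporting of pregnancies exposed during the study and follow-up of their outcome. The statistical results are not at stake.

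**Working it through.** The plan gives no calculated figure to reproduce. The check sets the stated windows side by side.

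**Inputs**
- Collection stop: 10 h after the last dose (8.3.1).
- Follow-up visit: 3 to 7 days after Visit 6 (4.1.5).
- Last study insulin: Visit 6 Day 1. The study pump is disconnected after the last meal-test samples (1.3.2, 4.1.3).
- Assumption: the last dose is taken as the end of Visit 6 Day 1.

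**Step 1: the cell read as a limit on detection**
- Earliest follow-up test: 3 × 24 = 72 h, and 72 − 10 = 62 h after the window closes (62 / 24 ≈ 2.6 days).
- Latest follow-up test: 7 × 24 = 168 h, and 168 − 10 = 158 h after it closes (158 / 24 ≈ 6.6 days).
- Clock times shift these figures. As a cautious bound, a visit on the third calendar day after Day 1 has two full days in between, so it falls at least 48 h after Day 1 ends, and 48 − 10 = 38 h.

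No permitted follow-up day falls inside the window.

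**Step 2: the cell read as a limit on onset**
A pregnancy that began inside the window and was found at Visit 7 would then be collected. One that began after the 10 hours but before Visit 7 would fall outside the table, yet it arises during participation and so falls under 8.3.2. The stretch on which the two texts disagree again runs from 10 h to the follow-up visit at 72 to 168 h, about 62 to 158 h.

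**Step 3: the pregnancy and complaint rows against the other rows**

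| Event | Stop in 8.3.1 | Other protocol text | Consistent? |
|---|---|---|---|
| Adverse event | Follow-up visit | Collected at Visit 7 (1.3.1) | Yes |
| Serious adverse event after start of intervention | End of participation | Runs on to the post-participation row | Yes |
| Pregnancy, female participant | 10 h after last dose | Test at Visit 7 (1.3.1, 10.4.2); all of participation (8.3.2) | No |
| Pregnancy, female partner | 10 h after last dose | None in 8.3.2 | Table is the only rule |
| Product complaint | End of study intervention | Collected at Visit 7 (1.3.1); next row starts at end of participation | Gap |

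**Step 4: which tests are affected**
Urine tests are also scheduled on Day -1 of Visits 3 to 6. Those at Visits 4, 5 and 6 follow study dosing in an earlier period and come before the last dose, so they fall inside the window. Only the test after the final dosing period is outside it.

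**The case against.** The strongest reply is that 8.3.2 already covers the case. The pregnancy row cites it, Visit 7 is a scheduled study visit, and 8.3.2 demands a 24-hour report and follow-up to outcome without any 10-hour limit. This stands for female participants. A reader might infer from the table that a positive Visit 7 test would go unreported, but the documents do not support that. They support only that two instructions disagree.

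A second reply is that the cell may define an exposure window by onset, with the reporting clock running from the time of learning. That is a reasonable reading, and the heading of the column does not settle it. On that reading the follow-up test does useful work for pregnancies that began in the window. The mismatch with the scope of 8.3.2 remains (Step 2), and the need to choose between the readings is itself a reason to clarify the cell.

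A third reply concerns product complaints. The schedule collects them at Visit 7, Sections 7.1 and 7.2 require their reporting or review when a participant stops early, and the study pump is no longer in use after Visit 6. This also stands, so it would be wrong to infer that complaints raised at Visit 7 are lost. What remains is an interval that the table assigns to no row, which matters for late reports of earlier problems.

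None of these replies helps with female partners. They have no study visit or study test, and the 8.3.2 text does not mention them.

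**Conclusion.** The 8.3.1 pregnancy stop conflicts with the protocol's own schedule and with the section it cites. On the detection reading it misses the only test scheduled after the final dosing period by about 62 to 158 h. On the onset reading it is narrower than 8.3.2 over the same stretch. Both figures assume that the last dose falls at the end of Visit 6 Day 1 and that visit days are counted as multiples of 24 h. The direction does not depend on exact clock times.

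For female participants the consequence is contradictory instructions and possibly missed or late reporting. For female partners, the 10-hour cell is the only rule given. The product-complaint gap is a smaller inconsistency of the same kind. Sample size, power and the primary analysis are unaffected. The point is worth correcting because it concerns a safety-collection rule.

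**What to change.** Reconcile the 8.3.1 table with 8.3.2, 4.1.5, 10.4.2 and the schedule in 1.3.1 in the next amendment:

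1. Set the pregnancy collection stop to the follow-up visit or the early discontinuation visit, and include the result of that visit's test.
2. State whether the window refers to onset or to detection of the pregnancy.
3. State the stop for female partners of male participants separately, since a rule tied to a visit and its test does not fit them.
4. Set the product-complaint stop to the follow-up visit.

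The cost is the pregnancy stop cell, the product-complaint stop (one change, entered in two rows) and a short clarifying note. No test, visit, sample or analysis is added.

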## 8.3.2. Pregnancy

#### **Collection of pregnancy information**

Female participants who become pregnant

- The investigator will collect pregnancy information on any female participant who becomes pregnant while participating in this study. The initial information will be recorded on the appropriate form and submitted to the sponsor within 24 hours of learning of a participant's pregnancy.
- The participant will be followed up to determine the outcome of the pregnancy. The investigator will collect follow-up information on the participant and the neonate, and the information will be forwarded to the sponsor. Generally, followup will not be required for longer than 6 to 8 weeks beyond the estimated delivery date. Any termination of pregnancy will be reported, regardless of gestational age, fetal status (presence or absence of anomalies) or indication for the procedure.

- While pregnancy itself is not considered to be an AE or SAE, any pregnancy complication or elective termination of a pregnancy for medical reasons will be reported as an AE or SAE.
- Any poststudy pregnancy-related SAE considered reasonably related to the study intervention by the investigator will be reported to the sponsor as described in Section 8.3.1. While the investigator is not obligated to actively seek this information in former study participants, he or she may learn of an SAE through spontaneous reporting.
- Any female participant who becomes pregnant while participating in the study will discontinue study intervention. If the participant is discontinued from the study, follow the standard discontinuation process and continue directly to the follow-up phase. The follow-up on the pregnancy outcome should continue independent of intervention or study discontinuation.

#### 8.3.3. Adverse Events of Special Interest

Not applicable.

## 8.4. Pharmacokinetics

At the visits and times specified in the SoA (Section 1.3), venous samples will be collected to determine the serum concentrations of insulin lispro. Instructions for the collection and handling of blood samples will be provided by the sponsor. The actual date and time (24-hour clock time) of each sampling will be recorded.

Samples collected for analyses of insulin lispro concentration may also be used to evaluate safety or pharmacology aspects related to concerns arising during the study.

Drug concentration information that would unblind the study will not be reported to CRU or blinded staff until the study has been unblinded.

#### 8.4.1. Bioanalysis

Samples will be analyzed at a laboratory approved by the sponsor and stored at a facility designated by the sponsor.

Concentrations of insulin lispro will be assayed using a validated enzyme-linked immunosorbent assay method specific for insulin lispro at a laboratory approved by the sponsor. Serum remaining may be used for other analyses on insulin lispro

Bioanalytical samples collected to measure investigational product concentrations will be retained for a maximum of 1 year following last participant visit for the study.

# 8.5. Pharmacodynamics

#### 8.5.1. Glucose Values

Blood will be collected for glucose values via **CC** at visits and times specified in the SoA (Section 1.3). These values will be used in statistical analyses, and the actual date and time (24-hour clock time) of each sampling will be recorded in the eCRF.

## 8.5.2. Exploratory CGM Values

For the CGM, a standard system (e.g., **CCL** ) will be used in this study. The study CGM sensor will be inserted by qualified CRU staff, and the participants will be instructed to always carry the receiver with them. The CGM device will be calibrated, if required, using the plasma glucose values obtained with the **CCL** by qualified CRU staff. Participants will not be allowed to view their glucose levels during the exercise or the liquid MMTT assessments. The participants will wear this device before the start of a standardized dinner (at **CCL** on Day -1 until completion of MMTT assessment on Day 1 for each in-house period. The monitor will record continuous glucose measurements. At the end of the recording, the study CGM sensor will be removed, and the receiver will be used to download the glucose data.

## 8.5.3. Exploratory Blood Ketones and Free Fatty Acids

Blood will be collected for ketones via CCl at visits and times specified in the SoA (Section 1.3). The actual date and time (24-hour clock time) of each sampling will be recorded in the eCRF.

Blood will be collected to determine concentration of free fatty acid levels at visits and times specified in the SoA (Section 1.3) using a validated method. The actual date and time (24-hour clock time) of each sampling will be recorded in the eCRF. Instructions for the collection and handling of these samples will be provided by the sponsor.

# 8.6. Genetics

Genetics are not evaluated in this study.

# 8.7. Biomarkers

Biomarkers are not evaluated in this study.

# 8.8. Immunogenicity Assessments

Not applicable.

# 8.9. Health Economics OR Medical Resource Utilization and Health Economics

Health economics or medical resource utilization and health economics parameters are not evaluated in this study.

## 9. Statistical Considerations

The SAP will be finalized prior to the first participant first visit, and it will include a more technical and detailed description of the statistical analyses described in this section. This section is a summary of the planned statistical analyses of the most important endpoints, including primary and key secondary endpoints.

